# 5.6 Statistical Analysis Methods

# 5.6.1. New User Analysis

The new user analysis (Ray 2003) will be based on a defined period of no insulin use prior to the first eligible prescription. To do so, all patients with a prescription of any insulin during the 19 months prior to the first eligible prescription will be excluded. The only exception will be for patients with only one prescription for a short-acting insulin. To allow for treatment titration and therefore better account for early switching, treatment augmentation, and non-chronic use, follow-up will not start at drug initiation but rather at the second prescription after initiation as outlined above. In cases where only one record is necessary to define the cohort (i.e. Ochsner and Partners HealthCare), follow-up will begin at drug initiation.

For the primary analysis, follow-up will start at the time-point defined above for all cohorts. To allow for time-varying hazard ratios (e.g., varying induction periods), we will stratify the follow-up into 0-<6 months, 6-<9 months, 9-<12 months, 12-<24 months, and 24+ months.

Augmentation with short-acting insulin during follow-up will be ignored for the primary analysis but will be described. To do so, time of a first prescription of a short-acting insulin will be ascertained as a separate variable (as well as specific formulation and dose).

The effect of cumulative insulin dose will be addressed by calculating the cumulative insulin dose as of every new prescription and categorizing patients into mutually exclusive categories of cumulative dose (e.g., >0-<=10kU, >10-<=20kU, >20-<=40kU, >40kU). We will categorize cumulative dose based on the long-acting insulin exclusively as well as on long-acting plus short-acting insulin combined. Time at risk for malignancies will start once a patient reaches the corresponding cumulative dose and end once a patient reaches the next cumulative dose level.

In the as treated new user design, follow-up time equals time on treatment since initiation and thus is an indicator of cumulative dose (while being less affected by intermediates). We will therefore also stratify follow-up time (e.g., 0-6, 6-12, 12-24, 24+ months; see above).

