# 5.6.2 Prevalent User Analysis and Other Subgroup and Sensitivity Analyses

In addition to the new user analysis described above, each group (UNC-CH and MedAssurant) will conduct an analysis of prevalent users using the same dataset that was used for the new user analysis, except patients with prescriptions for insulins prior to the first eligible prescription will not be excluded. Additional details about this analysis can be found in *Cohort study of insulin glargine and cancer risk among patients with diabetes mellitus (Kaiser Permanente, Northern and Southern California Regions)*. Results from the prevalent user analysis, including site-specific results and also combining across sites through meta-analysis, will also be reported. If the combined hazard ratios of glargine versus NPH differ substantially for the new user and prevalent user analyses for any of the four endpoints, then exploratory analyses will be carried out to explain the discrepancies.

For the new user analysis, sensitivity analyses will allow for varying latency periods of drug effects. To do so we will have additional variables censoring follow-up time 3 months, 6 months, 12 months, and 24 months after exposure defined censoring events (stopping, switching or augmenting) as described in Section 5.5. In these analyses, both events and person-time during these periods after stopping, switching, or augmenting will be counted towards the treatment preceeding these events. In addition, ITT analyses are also planned where we do not censor for augmentation, switching or stopping (i.e., counting all events until death or administrative censoring).

A complete list of planned subgroup and sensitivity analyses is included in Appendix C.

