Appendix C
Table of Planned Secondary and Sensitivity Analyses

Rank	Primary Analysis	Secondary Analyses	Rationale
Secondary Analyses			
1	Incident users	Perform analysis of prevalent users	Increase number of patients in study; confirm that results are similar to the new user analysis results.
2	All patients with diabetes	Exclude patients less than 40 years old or who do not have at least two prescriptions for oral hypoglycemic medications not more than 6 months apart during the baseline period.	Patients who meet these criteria will nearly all be Type II diabetics.
Sensitivity analyses			
1	Entire available follow-up	Stratify follow-up into 0-6 months, 6- 12 months, 12-24 months and >24 months after baseline	Allow for changing hazard ratios with time after initiation
2	Baseline (date of second prescription)	Begin follow-up 6 months, 9 months, 12 months and 24 months after baseline	Allow for varying induction periods  Note that this analysis is very similar but not exactly the same as the above

Rank	Primary Analysis	Secondary Analyses	Rationale
3	Censor immediately at stopping (plus grace period), switching, augmenting	Censor follow-up time 3 months, 6 months, 12 months and 24 months after a censoring event* (stopping, switching or augmenting). Both events and person-time during these periods after stopping, switching, augmenting will be counted towards the treatment preceding these events.  * Note that this applies only to censoring due to stopping, switching, augmenting; all other censoring (e.g., eligibility, calendar year) remain unchanged	Allow for varying latency periods for treatment effects
4	As treated	Do not censor follow-up time after a censoring event* (ITT analysis)  * Note that this applies only to censoring due to stopping, switching, augmenting; all other censoring (e.g., eligibility, calendar year) remain unchanged	Minimize the potential for selection bias
5	Exclude only non-overlapping propensity score regions	Exclude 1%, 2.5%. and 5% of those in the tails of the overlapping propensity score distribution, i.e., asymmetric trimming of those treated contrary to prediction	Most likely to have unmeasured confounders

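### The cumulative-dose analysis classifies events and person-time by current dose with zero lag, although the plan allows for induction and latency elsewhere, so its dose-response result is hard to interpret in either direction

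*Protocol*

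**What the plan says.** Section 5.6.1 of the protocol handles dose by "calculating the cumulative insulin dose as of every new prescription" and sorting patients into exclusive categories, with example cut-points "e.g., >0-<=10kU, >10-<=20kU, >20-<=40kU, >40kU". It fixes both ends of the risk interval: "Time at risk for malignancies will start once a patient reaches the corresponding cumulative dose", and it is to "end once a patient reaches the next cumulative dose level". Only the cut-points are marked as examples; the timing rule is not. The next paragraph offers a second route to dose, stating that "follow-up time equals time on treatment since initiation and thus is an indicator of cumulative dose", and stratifies on follow-up time.

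The protocol allows for delayed effects in other places:
- Section 5.6.1 divides follow-up into time bands so that the hazard ratio may vary with induction.
- Section 5.6.2 says that "sensitivity analyses will allow for varying latency periods of drug effects", by carrying follow-up on for 3, 6, 12 or 24 months after stopping, switching or augmenting.
- Appendix C, sensitivity analysis 2, reads "Begin follow-up 6 months, 9 months, 12 months and 24 months after baseline", with the rationale "Allow for varying induction periods".

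**The concern.** A tumour diagnosed soon after a patient crosses a dose threshold is assigned to the new category, although under any induction period the dose that matters is the one reached some months before. The delays listed above do not correct this. A later start of follow-up discards early person-time but leaves current dose in charge of the category. The carry-over rule acts only after treatment changes. Time bands are a separate stratification. Neither table in Appendix C contains a lagged-dose analysis, and section 5.6.2 presents that appendix as the full list of planned subgroup and sensitivity analyses.

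At stake is the reading of the dose-response result. A weak gradient might reflect misassigned dose rather than no effect, and a steep one might reflect dose increases that preceded diagnosis.

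**Working it through.** The protocol gives no power or effect figure for the dose analysis, so there is none to reproduce.

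**Inputs from the protocol.** Example cut-points of 10, 20 and 40 kU and the unlagged rule (5.6.1); median follow-up of about 2 years (section 6).

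**Assumptions not in the documents.** Constant daily dose U of 20, 40 or 80 U/day; exponential follow-up; constant baseline hazard; a true hazard ratio of 1.5 that begins one induction period L after 20 kU is reached; an unaffected reference category.

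**Check 1: the >20 to 40 kU category.**
- The category runs from day 20000/U to day 40000/U. At 40 U/day this is day 500 to day 1000.
- Attrition rate: k = ln 2 / 2 per year, or 0.693/730 = 0.00095 per day.
- Share of person-time past induction: f = [exp(−k(20000/U + L)) − exp(−k·40000/U)] / [exp(−k·20000/U) − exp(−k·40000/U)].
- Hazard ratio seen: 1 + 0.5f.

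At 40 U/day and L = 183 days, f = (0.523 − 0.387)/(0.622 − 0.387) = 0.578, so the hazard ratio is 1.29. At L = 365 days, f = (0.440 − 0.387)/(0.622 − 0.387) = 0.225, giving 1.11.

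| U/day | f, 6 months | HR seen | f, 12 months | HR seen |
|---|---|---|---|---|
| 20 | 0.740 | 1.37 | 0.522 | 1.26 |
| 40 | 0.578 | 1.29 | 0.225 | 1.11 |
| 80 | 0.245 | 1.12 | 0.000 | 1.00 |

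**Check 2: the >40 kU category in the same model.** At 40 U/day it begins on day 1000. Induction ends on day 500 + 183 = 683 or 500 + 365 = 865, so the full 1.50 is seen. At 20 U/day it is also 1.50. At 80 U/day the category begins on day 500. A 6-month induction ends on day 250 + 183 = 433, so 1.50 is seen. A 12-month induction ends on day 615, so f = exp(−0.00095 × 115) = 0.90 and the hazard ratio is about 1.45.

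**Check 3: a graded dose-response over all categories.** Further assumptions: daily dose lognormal with median 40 U/day and log-SD 0.5, follow-up capped at 72 months, true rate ratios 1.00/1.25/1.50/2.00 by lagged category.

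| Induction | Crude RRs, unlagged | RRs stratified by month, unlagged | Person-time in >10–20, >20–40, >40 kU whose lagged dose is in a lower category |
|---|---|---|---|
| 0 | 1.00/1.25/1.50/2.00 | 1.00/1.25/1.50/2.00 | 0% in each |
| 6 months | 1.00/1.08/1.38/1.88 | 1.00/1.03/1.21/1.58 | 69%, 44%, 23% |
| 12 months | 1.00/1.02/1.23/1.77 | 1.00/1.00/1.03/1.26 | 94%, 76%, 42% |
| 24 months | 1.00/1.00/1.06/1.51 | 1.00/1.00/1.00/1.01 | 100%, 97%, 71% |

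Lagging dose by the true induction time recovers 1.00/1.25/1.50/2.00 in every row. Cumulative dose never falls, so the lagged category is never above the current one. Under a monotone dose-response, ratios against the lowest category therefore move toward 1. This need not hold between upper categories: with 6-month induction the crude step from >10–20 to >40 kU is 1.88/1.08 = 1.74, against a true 2.00/1.25 = 1.60.

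**Check 4: dose rising before diagnosis.** With no true effect and an assumed 25% rise in daily dose over the 6 months before diagnosis, the unlagged month-stratified ratios in the three upper categories are 1.62/1.90/1.88. A 6-month lag gives 1.02/0.99/0.97.

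**The case against.** The best defence is that this is a subsidiary analysis. The objective and the main measure concern glargine against NPH, the dose paragraph is short, and Appendix C does not list the dose analysis at all, so the missing lagged version does not show that lags were considered and rejected. Section 5.6.1 also treats time on treatment as a stand-in for dose, and induction is examined on that scale. This limits the importance of the point but does not correct the dose categories: in check 3, stratifying by month of follow-up leaves the bias in place.

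Two points of reading also stand. The protocol does not say whether dose categories are compared with one another or glargine is compared with NPH within a category; the arithmetic above addresses only the first. And dose calculated at a new prescription may mean units from earlier fills, already largely used, so the text does not establish that patients are credited with insulin they have not yet injected.

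A reader might infer more than the documents support:
- **That a true dose-response must come out flat.** Check 2 leaves a visible gradient (about 1.29 or 1.11, then 1.50, at 40 U/day), and check 4 shows a bias in the opposite direction.
- **That dose-response is the plan's chief evidence on causation beyond the overall hazard ratio.** No section says so.
- **That 12 months should become the main lag, or that units must be recounted over days of supply.** The documents give no basis for either; both are preferences.

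**Conclusion.** The point holds in a limited form. The stated rule applies zero lag to dose in a plan that elsewhere allows for 3 to 24 months, and nothing listed tests that choice. If induction is not zero and the true dose-response is monotone, category hazard ratios against the lowest category are attenuated, most in the bounded middle categories. A true 1.5 in >20 to 40 kU appears as 1.12 to 1.37 with 6-month induction and 1.00 to 1.26 with 12-month induction over 20 to 80 U/day, while >40 kU shows 1.45 to 1.50. Under the graded model the top category is attenuated too. These sizes rest on daily doses, induction times and effects that the documents do not give; with zero induction this attenuation does not arise. Because dose escalation before diagnosis can create a false gradient, the net direction is uncertain. The primary glargine versus NPH hazard ratio is untouched, so this is a worthwhile correction to a secondary result and does not threaten the main one.

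**What to change.** In section 5.6.1 and Appendix C, add cumulative-dose analyses in which both events and person-time are assigned to the dose accumulated up to 6, 12 and 24 months earlier, intervals already used in Appendix C. Report them beside the unlagged version, and state that no dose-response conclusion will be drawn from the unlagged version alone. Say also where the first 6, 12 or 24 months go, since lagged dose is then zero and the lowest example category begins above zero; the calculations here put that time in the lowest category.

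The cost is programming for one derived time-varying variable and a few more runs, with no new data. Less person-time reaches the highest category, so its intervals widen. With a median follow-up of about 2 years, roughly half of the patients contribute no time beyond a 24-month lag, so that version will be the least precise.

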#### 5.4 Covariates

All covariates are defined based on available information within the 12-month period prior to and including the date of the first long-acting insulin prescription. It is important that this time is constant irrespective of the availability of additional data.

The minimum set of covariates includes age, gender, cohort entry date, co-morbidities (e.g., COPD as proxy for smoking), co-medication (including but not limited to other antidiabetic medications), health care system use (number of in- and outpatient encounters, days hospitalized), and screening behavior (especially cancer screening, see table). If available, smoking status, family history of cancer (overall and specific cancers, if available), body mass index, and duration of diabetes are also covariates of interest.

Potential confounders for specific types of cancers include use of hormone therapy and use of oral contraceptives.

Covariates by category are as follows:

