To adjust for potential confounding due to channeling between different long-acting insulins, we will estimate the propensity score for glargine initiation (primary analysis) and prevalent glargine use (secondary analyses) vs. glargine comparator initiation/use. In a first step, all covariates defined will be entered into the propensity score. Continuous or ordinal variables will be coded so as to be able to check

model assumptions (e.g., using dummy variables). Specific attention will be given to year of cohort entry because of the dynamics in channeling over time. Using complete cases only, we will empirically define the 10 covariates that are most strongly (Chi-square statistic) associated with channeling. We will then make a decision about whether these 10 covariates are risk factors for cancer based on substantive knowledge. We will then exclude covariates that are not risk factors for cancer. We will then re-estimate the propensity score based on the refined set of covariates. This re-estimated propensity score will be based on complete cases of the reduced set of retained covariates and thus may include more patients than the initial set of cases. Covariates in this re-estimated propensity score will be deemed confounders and we will thus exclude patients with missing values on these confounders to get an unbiased treatment effect estimate. If we lose more than 5% of our patients based on this strategy, we will consider multiple imputation methods of the covariates most strongly contributing to missingness before estimating the propensity score.

In addition, since BMI has the potential to be an important confounder given its association with the risk of breast and colon cancer, we will estimate the association between obesity (BMI >= 30 vs. < 30) and use of glargine vs. the glargine comparator. This estimate, in conjunction with information from the literature on the association between BMI and various cancer outcomes (Renehan et al., 2008) will be used to estimate the extent of potential confounding by unmeasured BMI in our main analyses (i.e. glargine vs. NPH and cancer risk) using a spreadsheet for unmeasured confounders developed by Schneeweiss et al (2005). We will use a cut point of a change in estimate of +/- 10% on the relative risk scale to define "relevant confounding by BMI" (Maldonado & Greenland, 1993).

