5	Estimate propensity score for glargine initiation over all calendar years	Estimate calendar-year specific rather than marginal propensity score models and run propensity score adjusted analyses stratified by calendar year	Allow for changes in treatment decisions over time other than increasing use of glargine
6	Censor patients at first occurrence of a nonspecific cancer code even if they have subsequent records for a specific cancer of interest	Ignore nonspecific cancer codes when defining incident colon, prostate or breast cancer cases	Confirm that results are similar

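### As worded, the propensity score can lose cancer risk factors from the plan's own minimum covariate set, and no clause keeps cohort-entry year in it

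*Protocol*

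**What the plan says.** Protocol Section 5.4 sets a floor for adjustment: "The minimum set of covariates includes age, gender, cohort entry date, co-morbidities (e.g., COPD as proxy for smoking), co-medication". Health care use and screening behaviour follow in the same list.

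Section 5.6.1 then builds the propensity score in steps:

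1. "In a first step, all covariates defined will be entered into the propensity score".
2. Calendar time is singled out: "Specific attention will be given to year of cohort entry because of the dynamics in channeling over time".
3. "Using complete cases only, we will empirically define the 10 covariates that are most strongly (Chi-square statistic) associated with channeling".
4. The analysts decide from subject knowledge whether these 10 are cancer risk factors. "We will then exclude covariates that are not risk factors for cancer".
5. "We will then re-estimate the propensity score based on the refined set of covariates".
6. "Covariates in this re-estimated propensity score will be deemed confounders". Patients with a missing value on any of them are excluded, and multiple imputation is considered if more than 5% of patients are lost.

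Later in the same section, balance is checked for covariates called important. Imbalance is weighed by its potential to affect the outcome. The Cox model controls for age, sex and anything still imbalanced.

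Section 5 has UNC-CH and MedAssurant each run the new user analysis, after which hazard ratios from the larger databases are pooled by inverse variance. In Appendix C, among the analyses to be done only if resources allow, stands: "Estimate calendar-year specific rather than marginal propensity score models and run propensity score adjusted analyses stratified by calendar year".

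**The concern.** A covariate confounds only if it is related to both treatment and cancer. The rule screens on treatment first and asks about cancer only for the covariates that pass. A moderate treatment predictor that is a strong cancer risk factor can rank 11th and never be asked about. A strong treatment predictor unrelated to cancer takes one of the 10 places and is then deleted.

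This sits badly with Section 5.4, whose minimum set has no protection in the selection steps. It matters most in the claims data. Appendix B lists only age and gender as claims demographics, with no BMI, smoking status or laboratory results, so COPD as smoking proxy, screening and health care use carry much of the remaining control.

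Cohort-entry year has a separate problem. The plan expects it to drive treatment choice, so it may well rank in the top 10. It then faces a test, whether it is a risk factor for cancer, that an analyst could reasonably answer either way.

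At stake is avoidable residual confounding in the primary hazard ratios of a non-randomised comparison, and pooling of estimates adjusted for different things.

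**Working it through.** The protocol gives no figure for this step, so there is nothing to reproduce. Three checks were made.

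**1. How many covariates the rule affects.** Counting Appendix B rows, with lipids as one:

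| | Claims | Ochsner | MGH |
|---|---|---|---|
| Demographic/baseline | 2 | 4 | 7 |
| Other medication | 24 | 24 | 24 |
| Laboratory | 0 | 7 | 7 |
| Co-morbidities | 5 | 5 | 5 |
| Health care use and screening | 10 | 10 | 10 |
| Total | 41 | 50 | 53 |
| Plus cohort entry date | 42 | 51 | 54 |

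- Capped reading (only the vetted top 10 can stay): at least 42 − 10 = 32 of 42 claims covariates leave the score, or 32/42 = 76%. Even if age and gender are two of these, 32 − 2 = 30 depend on the later balance check for any adjustment.
- Alternative reading (only non-risk factors among the 10 go): at most 10 leave and at least 32 stay.

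**2. Whether chi-square rank tracks confounding.** Group sizes are from Section 6: 47,227 glargine and 9,899 NPH. Prevalences (p1 glargine, p0 NPH) and relative risks are assumptions. With p the pooled prevalence:

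- chi-square = (p1 − p0)² / [p(1 − p)(1/47,227 + 1/9,899)]
- bias factor if omitted = [1 + (RR − 1)p1] / [1 + (RR − 1)p0]

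| p1 vs p0 | RR for cancer | Chi-square | Bias factor |
|---|---|---|---|
| 50% vs 40% | 1.05 | 328 | 1.025/1.020 = 1.005 |
| 30% vs 25% | 2 | 99 | 1.30/1.25 = 1.040 |
| 15% vs 12% | 3 | 59 | 1.30/1.24 = 1.048 |
| 30% vs 27% | 1.5 | 35 | 1.15/1.135 = 1.013 |

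The covariate with the highest chi-square has the least bias, and the third has the most. For the three with a relative risk of 1.5 or more, omitting one shifts the hazard ratio by about 1–5%.

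Several omitted together, independent and in the same direction:

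- five at 30% vs 25%, RR 1.5: (1.15/1.125)⁵ = 1.116
- eight at 30% vs 27%, RR 1.5: 1.013⁸ = 1.111 (unrounded ratio used)

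Both pass the 10% change that Section 5.6.1 uses, for BMI, as its mark of relevant confounding.

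**3. Whether sample size forces a cap of 10.** In MedAssurant, 9,899/42 ≈ 236 patients in the smaller group per covariate. Dummy coding raises the number of parameters, but size alone does not require a cap.

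**The case against.** **The cap is not stated.** No sentence removes covariates ranked 11th or lower, and the first step enters everything. The ranking could be a shortlist for deleting strong treatment predictors unrelated to cancer, which would be sound. This stands as a possible reading, so a flat statement that the plan limits the score to 10 goes too far. The capped reading fits better: everything left is called a confounder, yet lower-ranked covariates were never judged on cancer risk.

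**Leaving the score is not leaving the adjustment.** This also stands. Age and sex cannot be lost, and covariates found imbalanced are added, with attention to their effect on the outcome. A covariate at 40% vs 35% has a standardised difference of 0.05/√[(0.24 + 0.2275)/2] = 0.103, so a check at 0.1 would catch it. But 0.1 is an assumed limit. The plan sets none and does not name the covariates to be checked, so the safeguard is partial.

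**Entry year seems meant to stay.** A reader might infer that year will be deleted. The documents do not say so. Section 5.4 lists it, and the rationale for the calendar-year-specific score in Appendix C, to allow for changes other than the growth in glargine use, suggests the primary score already carries year. What stands is that no clause guarantees it.

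**Site differences are inferred.** A reader might conclude that adjustment does differ by site. The protocol is common to all sites and does not say the ranking is repeated in each. Separate analyses make differences possible, not certain.

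**The smaller set has a purpose.** The plan notes that fewer covariates can mean more complete cases. That is a real benefit, which the count of patients per covariate does not answer.

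**One score for both sexes.** A reader might add that breast and prostate analyses need their own scores. The text is silent and does not preclude them, so this is at most a secondary suggestion.

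**Conclusion.** The concern holds in a limited form. The protocol itself fixes a selection rule that, on its more natural reading, can drop minimum-set cancer risk factors from the score because they predict treatment only moderately. Under either reading cohort-entry year is unprotected. The balance check and Cox step reduce the problem without closing it. Two groups can apply these judgements differently before pooling.

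The count of at least 32 of 42 claims covariates depends on the capped reading and on counting Appendix B by row. The bias figures rest on assumed prevalences and relative risks, on independence from the retained covariates, and on no later correction. They show that a single omission is likely to be small and that several in one direction can matter. They do not estimate the bias in this study and do not show that its results would be wrong.

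**What to change.** In Section 5.6.1:

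- Keep in the propensity score, whatever the chi-square rank, cohort-entry year and every Section 5.4 minimum-set covariate that is a known or suspected cancer risk factor.
- Use the top-10 ranking only to flag strong treatment predictors with no link to cancer for removal, and say that covariates outside the top 10 are not removed by it.
- Use the same core set in the claims databases. Appendix B already gives them a single column.
- Name the covariates in the balance check and the threshold that sends one into the Cox model.

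The cost is a few sentences and minor programming. Weights may be slightly more variable, and complete cases possibly somewhat fewer. The plan's multiple-imputation provision, considered when more than 5% of patients would be lost, can address the latter.

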#### 5.3 Outcomes of Interest

Incident cases of new cancer will be identified from the respective databases. The three primary outcomes correspond to breast, prostate, and colon cancer individually. Only the primary cancer site will be used to determine whether the patient had breast, prostate or colon cancer. The secondary outcome will be all cancers combined excluding non-melanoma skin cancers. The only carcinoma in situ (CIS) cancers that will be included in the primary outcomes are cases of CIS breast cancer. For the analysis of claims data, an algorithm requiring two cancer diagnoses on different dates within a two month period will be required (Setoguchi et al, 2007).

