We will implement the propensity score by stratification (deciles) and inverse probability of treatment weighting (IPTW). Balance of important covariates will be assessed within deciles of the propensity score and in the weighted pseudo population. Any imbalance will be interpreted according to the potential of the imbalanced covariate to affect the risk for the outcome. Given balanced covariates and under the assumption of no unmeasured confounding, incidence rates and survival curves are adjusted or unconfounded and thus can be directly compared. Time trends in absolute and relative hazards will be assessed by stratifying on months of follow-up time (0-6, 6-12, 12-24, 24+). The main measure of association will be the hazard ratio estimated using a Cox proportional hazards model controlling for age and sex as well as any covariates remaining imbalanced after implementation of the propensity score.

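### The propensity score rule keeps a strong channeling covariate only if it is judged a cancer risk factor, which is too narrow when the claims outcome is a recorded diagnosis: screening and physician-visit variables may be dropped

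*Protocol*

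**What the plan says.** Section 5.6.1 of the protocol builds the propensity score in stages.

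- Start: "In a first step, all covariates defined will be entered into the propensity score".
- Empirical ranking, in complete cases: "we will empirically define the 10 covariates that are most strongly (Chi-square statistic) associated with channeling".
- Judgement: "We will then make a decision about whether these 10 covariates are risk factors for cancer based on substantive knowledge".
- Exclusion: "We will then exclude covariates that are not risk factors for cancer".

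The score is then re-estimated on the reduced set, and the covariates left in it are treated as the confounders.

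Three other places bear on this rule.

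- **Outcome.** For claims data, Section 5.3 says that "an algorithm requiring two cancer diagnoses on different dates within a two month period will be required".
- **Covariates.** The minimum set in Section 5.4 includes health care use and "screening behavior (especially cancer screening, see table"). The detailed list under that section names mammography, PSA and other screening tests, and outpatient physician encounters. The claims column of Appendix B carries PSA, mammography, endoscopy, Pap smear and physician visits.
- **After the score is applied.** Later in Section 5.6.1, balance is checked for important covariates, and "Any imbalance will be interpreted according to the potential of the imbalanced covariate to affect the risk for the outcome". The Cox model adjusts for age, sex and whatever covariates are still imbalanced. Incidence rates and survival curves may be compared directly, on condition that covariates are balanced and there is no unmeasured confounding.

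**The concern.** The purpose of the exclusion step is sound: a variable that predicts only treatment adds variance to the score and removes no confounding. The fault is in the test used to identify such variables. A covariate confounds the hazard ratio if it is related to insulin choice and to the outcome as measured. In claims, the outcome as measured is a pair of diagnosis codes. PSA testing, mammography and frequent physician contact change the chance and the timing of those codes, whether or not they have any causal role in cancer. A test that asks only about cancer risk factors can therefore discard a true confounder, and it is applied to the covariates that channel most strongly.

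At stake is detection bias in the glargine versus NPH comparison. Breast and prostate cancer, two of the three primary outcomes, have their own screening tests on the covariate list. Section 5 relies on the MedAssurant claims data for sufficient power, so the claims outcome carries most of the weight.

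**Working it through.** The protocol gives no figure for this point, so there is nothing to reproduce. The check has two parts.

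**1. The criteria side by side**

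| Place in protocol | Criterion or content | Would a determinant of detection pass? |
|---|---|---|
| 5.3, claims outcome | Two recorded diagnoses on different dates | It affects this outcome |
| 5.4, minimum set | Screening and health care use included | Yes, named |
| 5.6.1, exclusion step | Risk factor for cancer | Not on a literal reading |
| 5.6.1, reading of imbalance | Potential to affect risk for the outcome | Yes, on a fair reading |

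The exclusion step is the narrowest of the four, and it is the one that fixes the content of the final score.

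**2. Possible size of the bias**

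Take one binary covariate (screened or not) that is left wholly unadjusted, with no true treatment effect. Let p1 and p0 be the proportions screened among glargine and NPH starters, and R the ratio of diagnosis rates, screened to unscreened. Then

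bias factor = [1 + p1(R − 1)] / [1 + p0(R − 1)].

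The documents give none of these inputs. The values below are assumptions.

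| p1 vs p0 | R = 1.5 | R = 2 | R = 3 |
|---|---|---|---|
| 50% vs 40% | 1.25/1.20 = 1.04 | 1.50/1.40 = 1.07 | 2.00/1.80 = 1.11 |
| 55% vs 40% | 1.275/1.20 = 1.06 | 1.55/1.40 = 1.11 | 2.10/1.80 = 1.17 |

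The result is not very sensitive to the base proportion. With 30% screened among NPH starters, a 10-point difference gives 1.04, 1.08 and 1.13, and a 15-point difference gives 1.07, 1.12 and 1.19. At the edges, 35% vs 30% with R = 1.2 gives 1.01, and 50% vs 30% with R = 3 gives 1.25.

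The sign depends on which group is screened more. If NPH starters were the more screened, the main-table range would invert to 1.20/1.25 = 0.96 through 1.80/2.10 = 0.86.

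For scale, Section 5.6.1 treats a change of 10% in the relative risk as relevant confounding, though it says so for BMI only. Three of the six main-table values exceed that mark and three do not.

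**The case against.** The strongest reply is that the protocol nowhere says these variables will be removed. The exclusion rests on a judgement from substantive knowledge, stated for the top ten only. The text does not clearly say what happens to covariates outside the ten. Authors who put screening in the minimum set might well count it as a risk factor. This stands: a reader might infer that the score must drop screening and health care use, but the documents support only that it may.

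A reader might also infer that the smoking proxy is lost. The documents point the other way. Section 5.4 lists "co-morbidities (e.g., COPD as proxy for smoking"), so COPD was chosen because it stands for a cancer risk factor, and a substantive test would most naturally keep it. The claims column of Appendix B also carries respiratory drugs that may mark the same disease. The concern should not rest on COPD.

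The Cox step is a real safeguard. A strong channeling variable left out of the score is likely to remain imbalanced, the imbalance is read against risk for the outcome, and the model then adjusts for it. The comparison of rates and curves is expressly conditional on balance. Two gaps remain. Balance is checked for covariates deemed important, and one just set aside as not a risk factor may not be checked. And adjustment in the Cox model does nothing for the weighted incidence rates and survival curves: if the dropped covariate is imbalanced, the condition for comparing them fails and the plan offers no correction.

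Finally, covariate lists are often settled in a statistical analysis plan. That is fair for the list, but the exclusion criterion is already fixed in the protocol.

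**Conclusion.** The criterion is too narrow for a diagnosis-based outcome and sits badly with the protocol's own minimum covariate set and with its wider wording on imbalance. Strong channeling variables that act through detection, chiefly cancer screening and physician-visit counts, may be left out of the re-estimated score, and the later Cox adjustment protects against this only in part.

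The size and direction of any resulting bias are unknown. Under the assumed 10 to 15 point differences from a 40% base and diagnosis-rate ratios of 1.5 to 3, a null hazard ratio would become about 1.04 to 1.17. These figures assume glargine starters are the more screened and that there is no adjustment at all, so they overstate the effect wherever the Cox step works.

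It is tempting to set this range against the minimum detectable ratio of 1.2 in Section 6. That figure is for any cancer, whereas the concern is sharpest for breast and prostate cancer, where the figures are 1.53 and 1.58. Mammography or PSA testing would affect only part of the all-cancer endpoint. The documents do not support a claim that the bias would reach a detectable effect. The point is a wording fault in an operative rule, worth correcting because the correction is cheap.

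**What to change.** Replace the exclusion sentence in Section 5.6.1 with wording such as: *Only covariates judged unrelated to the recorded cancer outcome will be dropped, that is, those that are neither risk factors for it, nor proxies for a risk factor, nor determinants of its detection.* Add that the cancer-screening variables and physician-visit counts are retained in the re-estimated score.

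This need not extend to the whole health-care-use category. Variables that plausibly predict treatment only, for example lipid assessments or ECGs, may still be dropped, which preserves the purpose of the step.

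The cost is a few lines of text. The covariates are already planned for every data source in Appendix B. The one downside is that a few more covariates in the score may slightly widen the weighted intervals.
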